## A. BACKGROUND & SIGNIFICANCE

The primary goal of this research project is to improve the health status and decrease hospitalization and death for patients discharged with heart failure (HF) via self-management education to patients, disease monitoring and medication titration through shared medical appointments (SMAs). Significance & Scope of the Problem

HF currently affects 5.1 million people in the US and 825,000 new HF cases are being diagnosed annually. HF is a leading cause of cardiovascular disease morbidity and mortality worldwide, costing 1-2% of the total healthcare budget in developed countries. In 2009 alone, 1 in 9 deaths in the US cited HF as a contributing cause. Half of Americans who develop HF die within 5 years of diagnosis and more than one third of HF patients require frequent hospitalizations, or placement in long term care. HF has a particularly higher impact among older people ( $\geq 65$  years old) and those with multiple co-existing illness, with  $\geq 90\%$  of HF-related deaths to occur among people  $\geq 65$  years. With 1 in 10 elderly living with HF and an aging population in the US, HF mortality and morbidity greatly impacts the health of our Veteran population. Indeed, our preliminary data from a random cohort of  $>100,000$  patients admitted with HF at VHA hospitals nationwide, showed the HF veteran population to be elderly (average age = 71 years), and has 30-day and one-year mortality rates of 6 and 30%, respectively, after their hospitalization. Since the main goal of the VHA is to improve health of the veterans, patient-reported health status is an important outcome metric for HF patients that includes symptom burden, functional status and health-related-quality-of-life, and an independent predictor of mortality, cardiovascular events, hospitalization and cost of care. HF patients have a significant impairment of health status, in both physical and mental health, in addition to declines in functional status.

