#### **6. HF-SMA at Phoenix VA Hospital:** The Phoenix VA instituted weekly HF-SMA in 2013 with capacity

to see 4-6 patients in each session. [name] oversees the HF-SMA in case of difficult patient scenarios. Data on 54 patients referred to this program showed a patient population with a median age of 66 years, 82% White, 100% male, with a mean left ventricular ejection fraction of 35%, and the median number of medications = 10. Preliminary results after SMA showed a 90-day readmission rate of 7% and mortality of 4%, which is in contrast to the 25% 30-day readmission rate for Phoenix patients with a recent HF discharge (FY2014).

Focus groups conducted with patients after HF SMA suggested that the patients liked the open forum format and they believed SMA helped because it addressed a broad spectrum of concerns, provided additional medical information and strategies for coping with illness, had more time to talk with healthcare team, explored questions more deeply/reflect on answers, the conversation-like setting and support group' environment ("Not alone") and the learning from other patients' questions/ experiences as well as opportunity to share own experiences. Among the concerns expressed, one patient expressed that others were judging him and inhibited his openness going forward and another patient expressed: *"Group providers and patients don't know me as well and not a safe environment to voice personal issues as they can be misconstrued"*; *"your personal doctor isn't there"*. These are important lessons learned to control group dynamics and avoid stigmatization, earn the trust and have guidelines for participation to protect privacy. Some patients needed clarification on whether SMA is meant to replace visits to doctors (possible misunderstanding among new SMA patients about

the role their SMA provider plays). In our current model, the patients are advised that all treatment plans are communicated back to their primary providers via CPRS (provider decision support).

Overall, the above data support the feasibility of SMAs in HF, experience of the team in RCTs and multi-site studies. However, the effectiveness of HF-SMA in improving patient outcomes is still unknown despite strong theoretical underpinnings, and further investigation is warranted.

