**5. Randomization and retention:** Once enrolled, patients will be randomly assigned on a 1:1 ratio to intervention or placebo arms using a stratified block randomization method with block sizes of 4 in each site to ensure balance of the stratified variables. Stratification will be based on the study site and the presence or not of: a) co-intervention (enrollment to HF clinic, support group or education), b) ≤2 hospitalizations in the last 6 months, and c) left ventricular ejection fraction <40%. Randomization will be done by the call-in method to a central computer administered by the study coordinator at Providence VAMC, the coordinating site. To ensure subject safety and continuous engagement in study procedures, patients will be called by phone by study staff on a monthly basis following randomization to answer any questions that may arise, ask for participation in HF programs and doctor's visits, ER visits, document adverse events and maintain study engagement. Patients in the control arm will be invited to participate in HF-SMAs at the end of the study, to honor patient's preferences.

Our preliminary data showed that our recruitment in prior SMA research has been successful, ~50-60% of those screened and eligible agreed to enroll in SMAs; and then about 90% of those enrolled finished the study. Reasons for drop out are: geographic mobility, change in work schedule, incarceration, and homelessness. Yet, we have been able to maintain a good retention rate, through a combination of excellent relationships with participants, and a perceived value of the study to clients.

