Sample Size and Power Considerations: The overall study sample will be 375 (225 patients from Phoenix VAMC and 150 patients from Providence VAMC). Statistical power for the aims 1 and 2 is estimated given these are the most relevant and the most restrictive in terms of power estimations. Under a conservative dropout rate of 15% for 180 days of follow-up for the main outcomes (Aims 1 and 2), we estimate the power with an effective sample size of 316 (15% less than the total sample) and a 2-sided significance level of 0.05 using nQUERY Advisor 7.0®. For aim 1, we assess the power to detect a clinically significant change in KCCQ of 5 points, assuming a baseline score of 63 (our preliminary studies), with a common standard deviation of 15 for the study arms, using a 2-sample t-test. For aim 2, we assess the power to detect a relevant decrease in rehospitalization or death risk of 25-30% at 180 days using a Cox Proportional Hazards model. Based on our preliminary data of 20,000 Veterans with ejection fraction <40% hospitalized with HF, their rehospitalization rates at 6 months is ~40%. Assuming similar event rates for rehospitalization or death, as shown in Table 2, we have good power to detect the proposed outcomes at very conservative estimates of effective sample size (n=158 in each arm, which is 85% of the total proposed recruitment target). Repeated measures at 90 and 180 days are also likely to add to the statistical power in Aim 1 to detect differences at the subgroup levels.

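### The 15% loss allowance is not conservative for the day-180 KCCQ once the plan's own mortality figures are added, and the imputation rule makes no exception for patients who die

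*Combined protocol and SAP*

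**What the plan says.** All places are in the combined protocol and SAP.

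- **Sample Size and Power Considerations** (in 9. Quantitative Analytic Plan): "The overall study sample will be 375". The allowance is "Under a conservative dropout rate of 15% for 180 days of follow-up for the main outcomes (Aims 1 and 2"), giving an "effective sample size of 316 (15% less than the total sample"), or "n=158 in each arm, which is 85% of the total proposed recruitment target". The text does not say whether dropout includes death.
- **Table 2**: Aim 1 power at 180 days is 0.76 for 4.5 points and 0.84 for 5 points.
- **5. Randomization and retention**: in earlier shared-appointment research "about 90% of those enrolled finished the study". The reasons listed for dropping out are moving away, work schedules, incarceration and homelessness.
- **A. Background & Significance**: a national VHA cohort admitted with HF had "30-day and one-year mortality rates of 6 and 30%, respectively, after their hospitalization".
- **Preliminary work, item 6 (Phoenix)**: among 54 patients referred to the HF-SMA programme, "a 90-day readmission rate of 7% and mortality of 4" per cent.
- **Aims 1 and 2** (in 9. Quantitative Analytic Plan): KCCQ is analysed by a linear mixed model on baseline, 90-day and 180-day scores. Death is an event in the Aim 2 composite.
- **Missing Data Issues** (same section): reasons for missing data will be recorded. Values are imputed if missingness is judged random, and if attrition differs between arms the intention-to-treat analysis fills gaps with randomly generated values. Neither place gives a rule for KCCQ after death.

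**The concern.** The only visible basis for the 15% is the roughly 10% non-completion in earlier work, plus a margin of five percentage points. The earlier trials described under preliminary work were in diabetes, and the background section itself contrasts that disease with HF, where decline or death is a constant risk. Deaths therefore have to fit inside the five-point margin, and the plan's mortality figures suggest that they will not. Calling the allowance conservative tells the reader that the stated power has slack when it has none.

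The second issue concerns meaning rather than sample size. A KCCQ score after death does not exist. If gaps are filled without regard to cause, the primary comparison describes a hypothetical population in which nobody died. Aim 2 hypothesises fewer hospitalizations or deaths with HF-SMA, so survival may differ by arm. A comparison that imputes the dead, or that silently covers survivors only, could then mislead in either direction.

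**Working it through.** **1. Reproduce the stated power.** Inputs from the sample size section: 158 per arm, difference 5, SD 15, two-sample t-test, "a 2-sided significance level of 0.05". The noncentrality parameter is 5 / (15 × √(2/158)) = 2.963, and the noncentral t distribution gives power 0.840. For 4.5 points it gives 0.758. Both agree with Table 2. (0.85 × 375 = 318.75, so 316 is a loss of 15.7%; the difference is immaterial.)

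**2. Mortality over 180 days.**

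- Phoenix pilot, constant hazard: 1 − 0.96² = 0.078, taken as 8%. This is 0.08 × 375 = 30 deaths.
- National cohort, constant hazard from day 30 to day 365: −ln(0.70/0.94)/335 = 0.000880 per day. Over 180 days, 1 − exp(−0.000880 × 180) = 0.1465, about 55 deaths.

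Starting at day 30 fits the Providence experience in the preliminary work, where patients often put off attending until three to four weeks after discharge. Two cruder readings of the national figures give 16.1% (constant hazard over the whole year) and 17.6% (clock starting at discharge). With 10% dropout they give power of 0.78-0.80. I do not use them because they count early deaths that most enrolled patients will already have survived.

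**3. Add the plan's non-death dropout of 10%.** Dropout can apply to survivors only (loss = 1 − (1 − m)(0.90)) or be added outright (loss = m + 0.10). N = 375 × (1 − loss), split equally between arms, SD 15, noncentral t:

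| Mortality m | Combination | Total loss | N with day-180 KCCQ | Power, 5 points | Power, 4.5 points |
|---|---|---|---|---|---|
| As stated in plan | – | 15.7% | 316 | 0.84 | 0.76 |
| 8% (Phoenix) | survivors only | 17.2% | 310 | 0.833 | 0.750 |
| 8% (Phoenix) | added | 18.0% | 307 | 0.830 | 0.746 |
| 14.65% (national) | survivors only | 23.2% | 288 | 0.805 | 0.718 |
| 14.65% (national) | added | 24.65% | 283 | 0.797 | 0.710 |

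**4. Threshold.** Power for 5 points stays at or above 0.80 down to 143 per arm: 1 − 286/375 = 23.7% total loss.

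**5. Deaths in the imputation text.** The mixed model uses whatever scores exist and treats the rest as missing at random. The missing-data text fills gaps under stated conditions (randomness, unequal attrition), and none of these depends on whether the patient was alive. Recording the reason for a missing value does not change what is done with it.

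**The case against.** The best opposing case is that this is a dispute about an assumption, and the effect is small. Much of that stands.

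- **The 0.84 is correct for its inputs.** A reader might infer an arithmetic error. There is none.
- **National mortality is probably too high for this trial.** The exclusion criteria remove hospice, long-term nursing home, comfort-only, dialysis, inotrope and ventricular-assist patients, and enrolment may come up to 12 weeks after discharge. The 15% figure is therefore an upper bound. The Phoenix figure is closer to the trial population but rests on about two deaths among 54 patients.
- **The t-test is not the planned analysis.** In the mixed model a patient who dies after day 90 still contributes data, so some power may be recovered. The documents do not quantify this.

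Three stronger readings are tempting and not supported. First, that 15% leaves no room for deaths: it leaves five points above the historic 10%, and on the Phoenix figure total loss exceeds the allowance by only two or three points. Second, that power falls to 0.78: with day-30 national mortality this needs the full 15% as non-death loss, whereas the documents' own dropout figure is 10%. Third, that deaths are wrongly removed from Aim 2: the Cox analysis counts death as an event and censors only patients without one, so nothing there needs correcting.

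A reader might also infer that the plan intends to impute scores for the dead. It does not say so. The text is silent, and imputation is conditional. Nor would deaths go unseen, since the Aim 2 composite includes them at 90 and 180 days. That does not supply the missing rule for the primary outcome.

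**Conclusion.** The concern holds in moderate form. On the plan's own dropout and mortality figures, about 17-25% of patients would lack a day-180 KCCQ, against the stated 15%. Power for 5 points is then about 0.80-0.83 instead of 0.84, an overstatement of one to four percentage points; for 4.5 points it is 0.71-0.75 instead of 0.76. The trial is not badly undersized on this account, but the allowance should not be called conservative.

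The gap in the rule for deaths is the stronger reason to act, because it affects what the primary comparison means whatever the power.

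These figures assume constant hazards, equal loss in both arms, 10% non-death dropout, SD 15, and a day-180 t-test that ignores earlier scores.

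**What to change.** 1. In the sample size section, state expected death and other loss separately for Aim 1. Give the day-180 KCCQ sample as about 283-310 and power as about 0.80-0.83 for 5 points (0.71-0.75 for 4.5), and drop the description of the allowance as conservative.
2. In Missing Data Issues, exclude from imputation any KCCQ score due after a patient's death, and say what the mixed-model estimate then represents.
3. Prespecify one sensitivity analysis of day-180 KCCQ in which patients who die before that assessment rank below all survivors, for example a Wilcoxon test stratified by site. State how survivors without a score are handled. Report it beside the Aim 2 result, with the number of deaths by arm.

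Aim 2 needs no change on this point. The cost is slightly less favourable stated power and one extra analysis. Table 1 already schedules both KCCQ and deaths, so no new data are needed.

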8. Study Visits, Data Collection and Study Outcomes: There will be 3 research visits: 1) baseline for enrollment consent and data collection, and 2) at 90 days (+ or - 30 days) and 3) at 180 days (+ or - 30 days) after randomization for outcome collection, in addition to monthly phone calls in between study visits. All surveys will be self-administered unless the patient prefers otherwise. Only experienced interviewers will conduct the interviews, proficiency must be demonstrated to site PI. Training for the qualitative aspects of the study will be provided by the Cleveland site. All patient self-reported measures and interviews will be performed during the three research study visits. To accommodate patients, per request, study visits may be conducted over the phone or in a private location of their choosing with two study members present. Also to further accommodate patients, per request, de-identified surveys using only a study ID number may be mailed out along with a postage paid, self addressed return envelope. Patients will be instructed not to include their name on any of the returned surveys. Research assistants must demonstrate proficiency in data collection techniques to the site PI's.

Aim 1: Primary outcome is change in KCCQ and secondary is change in EQ5D.

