Kansas City Cardiomyopathy Questionnaire (KCCQ)(Appendix): is a 23 item instrument validated in stable and decompensated HF patients with preserved or reduced ejection fraction. The questionnaire takes 4-6 minutes to complete, and reflects disease-specific health status over the prior two weeks. The domains of KCCQ are physical limitation, symptoms, self-efficacy, social limitation, and quality of life. The domains of the KCCQ have a high internal consistency with a Cronbach's alpha of 0.95 for the Overall Summary Score and  $\geq 0.62$  for all individual scales. The KCCQ has a significantly higher responsiveness to changes in health status than the Minnesota Living with Heart Failure Questionnaire and the SF-36. The overall summary score is 0-100 where higher score is better. The minimal clinically important change in survey score is 5 points, with a 10- and 20-point change reflecting moderate and large clinical changes, respectively. In the Eplerenone Post-AMI Heart Failure Efficacy and Survival Trial (EPHESUS), each 5-point decline in KCCQ Overall Summary Score on serial assessments was associated with a hazard ratio of 1.11 (95% CI, 1.05-1.17) for subsequent cardiovascular death or hospitalization. Preliminary data from Phoenix VA found a median Summary Score of  $52.4 \pm 27.8$  (n =32) in HF-SMA participants indicating fair/poor health status.

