#### 9. Quantitative Analytic Plan:

Aim 1: To compare between the intervention versus usual care arms in the change from baseline in KCCQ (Primary outcome) and EQ5D (secondary outcome) at 90 and 180 days. The analysis will be performed from an intention to treat principle. First, descriptive statistics (mean, standard deviation, median, inter-quartile range, and frequency distribution) will be calculated to summarize, at baseline, patients' demographic and comorbidities including previous hospitalizations, cardiac history (heart function and coronary disease), medical and health service utilization information (including medication possession ratio, HF self-care index, BNP levels, enrollment into HF clinics / programs, visits with primary care and cardiologists), and the primary outcome of interest (KCCQ, overall score) according to randomized arms. Log-transformation of variables and outcomes of interest will be performed to approximate normality when appropriate. Linear mixed-effects (LME) model will be utilized for the analysis of this aim, where the response variable is KCCQ, fixed effects include treatment group, time (0 = baseline, 1 = at 90 days, 2 = 180 days), treatment group by time interaction, and other important demographic variables identified in the descriptive analysis, and random effects include site-specific random intercept, subject-specific random intercept (nested within site) and subject-specific random slope of time. This modeling approach has been shown to provide an unbiased and efficient estimate of the longitudinal treatment effect in a variety of situations, such as in the presence of missing data, imbalance of the primary outcome at baseline, and covariance heterogeneity between treatment groups. In this way, we could compare the intervention effects at 90 days and whether residual effects exist at 180 days. The random site effect is used to model the clustering effect of patients in the same study site and random subject effects are used to model the variability in the subject-specific trajectory and the correlation of repeated measures within subject. Residual analysis will be conducted to examine the appropriateness of the functional forms of each fixed effect, and Information criteria (AIC, BIC) will be used to choose the correlation structure.

Secondary: Same modeling technique will be used to study EQ5D as the outcome instead of KCCQ.

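### Aim 1's power of 0.84 depends on a KCCQ standard deviation of 15 whose source and scale are not shown, and which is not reconciled with the only KCCQ spread the protocol reports

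*Combined protocol and SAP*

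**What the plan says.** Section 9 of the study design (Quantitative Analytic Plan), under Sample Size and Power Considerations, uses a two-sample t-test at two-sided 0.05 with 158 evaluable patients per arm, "assuming a baseline score of 63 (our preliminary studies), with a common standard deviation of 15 for the study arms". Table 2 gives Aim 1 power at 180 days of .76, .84, .90 and .95 for mean differences of 4.5, 5, 5.5 and 6 points. The text concludes that "we have good power to detect the proposed outcomes at very conservative estimates of effective sample size".

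Section 8 (Study Visits, Data Collection and Study Outcomes) defines the endpoint: "Primary outcome is change in KCCQ and secondary is change in EQ5D". The KCCQ description there says "The minimal clinically important change in survey score is 5 points". It also gives the protocol's only KCCQ spread: "Preliminary data from Phoenix VA found a median Summary Score of" 52.4 ± 27.8 in 32 participants in the heart failure shared appointments.

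For the analysis of Aim 1, section 9 specifies a linear mixed model in which baseline is one of the response times: "fixed effects include treatment group, time (0 = baseline, 1 = at 90 days, 2 = 180 days), treatment group by time interaction". The 180-day interaction contrast in that model is a between-arm difference in change from baseline.

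**The concern.** Three things are left open about one number.

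- **Source.** The note on preliminary studies follows the baseline of 63. No dataset or citation is shown for 15.
- **Scale.** Fifteen could be the SD of a single score or of change from baseline. These imply different power for the same trial, and Table 2 labels its column only as a difference in mean KCCQ.
- **Consistency.** The power section mentions neither 27.8 nor 52.4. The pilot comes from Phoenix, which is to supply 225 of the 375 patients. The baseline does not enter the t-test power, but the gap between 63 and 52.4 suggests that planning used data the supplied text does not show.

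Table 2 is the only power support for the primary outcome. If the relevant SD is well above 15, the trial could miss a difference the protocol calls clinically important. A null result might then be unable to rule that difference out.

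**Working it through.** **Inputs.** From section 9: difference 5, SD 15, n = 158 per arm, two-sided 0.05. From the KCCQ description in section 8: 27.8, n = 32. The documents give no correlation between baseline and 180 days, so every correlation r below is an assumption.

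**1. Reproduce Table 2.** The standard error is 15 × √(2/158) = 1.688. The noncentrality is 5/1.688 = 2.963, and the critical t on 314 df is 1.968. Power is 0.840. The rows for 4.5, 5, 5.5 and 6 points give 0.758, 0.840, 0.901 and 0.943, against .76, .84, .90 and .95 in the table. The arithmetic is sound.

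**2. Slack.** With the same formula, the largest SD that keeps 80% power for 5 points is 15.8, about 5% above 15.

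**3. What 27.8 could be.**
- *An SD.* With n = 32 and normal data, the chi-square 95% interval is 22.3 to 37.0. This excludes 15 as the SD of scores in that population.
- *An interquartile width*, which the word median invites. The SD is then about 27.8/1.349 = 20.6 under normality. With 32 patients, the simulated 95% interval for the SD reaches down to about 14 to 15, so 15 is not clearly excluded.

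**4. Correlation needed for 15 to be the SD of change.** With equal SDs at both visits, SD of change = SD × √(2(1 − r)), so r = 1 − 15²/(2 × SD²).
- SD 20.6: 1 − 225/(2 × 424.8) = 0.74
- SD 27.8: 1 − 225/(2 × 772.8) = 0.85

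For 80% power, where the SD of change may be as high as 15.8, the values are 0.71 and 0.84.

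**5. Power for the 180-day difference in change** (5 points, 158 per arm). The SD of change is in brackets.

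| Score SD | r = 0.6 | r = 0.7 | r = 0.8 |
|---|---|---|---|
| 20.6 | 0.67 (18.4) | 0.79 (16.0) | 0.92 (13.0) |
| 27.8 | 0.43 (24.9) | 0.54 (21.5) | 0.71 (17.6) |

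The plan's own t-test, applied to scores, gives 0.58 at SD 20.6 and 0.36 at SD 27.8. If 15 were instead the SD of scores, the change contrast would do better than Table 2: 0.91 at r = 0.6 and 0.97 at r = 0.7. The missing scale therefore cuts both ways.

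**6. Precision of the change contrast.** The 95% half-width is 1.968 × SD of change × √(2/158). At r = 0.6 and 0.7 it is 4.1 and 3.5 points for SD 20.6, and 5.5 and 4.8 for SD 27.8. Of these four cases, only SD 27.8 with r = 0.6 would leave an estimate of zero unable to exclude 5 points.

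**The case against.** The best defence is that 15 is the SD of change. The power paragraph speaks of a change of 5 points and the endpoint is change. On that reading 15 is not comparable with a cross-sectional 27.8, and 0.84 already is the power of the planned contrast. The parenthesis on preliminary studies could also be read to cover both the 63 and the 15, with data lying outside the supplied text. The pilot is small, comes from one site, and attaches ± to a median. All of this stands, and it is why the SD cannot be called wrong. None of it supplies the missing statement of source, scale or correlation.

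A reader might go further and infer that the trial is underpowered, with a true power of 0.36. The documents do not support that. The figures 0.36 and 0.58 apply to a t-test on scores, whereas the planned contrast is a difference in change. On the interquartile reading, a correlation of 0.7 already gives 0.79.

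It may also be said that the design has reserves. They exist but are modest:
- Keeping 90-day data from patients lost later (375 randomised, 15% lost after day 90, equal correlations) gives 0.70 to 0.82 at SD 20.6 and 0.45 to 0.56 at SD 27.8, for r of 0.6 to 0.7.
- Section 5 reports that in earlier work "about 90% of those enrolled finished the study". At 10% loss, 169 per arm, the t-test on scores rises only to 0.60 and 0.38.
- The remark that "Repeated measures at 90 and 180 days are also likely to add to the statistical power in Aim 1" goes on to confine the gain to subgroup differences and gives no figure. It should not be read as a claim about the main comparison.

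**Conclusion.** The concern holds as an unsupported and unreconciled planning assumption. It is neither an arithmetic error nor demonstrated underpowering. The 0.84 follows from SD 15, but 80% power is lost once the relevant SD exceeds 15.8. Agreement with the pilot needs a baseline-to-180-day correlation of about 0.74 to 0.85, depending on what 27.8 means.

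Over assumed correlations of 0.6 to 0.8, power for the change contrast runs from 0.67 to 0.92 on the more favourable reading of the pilot and from 0.43 to 0.71 on the less favourable one. These ranges assume normal data, equal SDs at baseline and 180 days, and 158 evaluable patients per arm. They also assume that the pilot spread applies to the trial population, which the documents do not establish. The unqualified conclusion of good power for 5 points is therefore stronger than the text supports.

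**What to change.** In Sample Size and Power Considerations:

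1. Give the source of SD 15 and say whether it is an SD of scores or of change.
2. In the KCCQ description, say what ± 27.8 is. Reconcile the pilot's 52.4 with the assumed baseline of 63.
3. Restate the Aim 1 column of Table 2 for the planned 180-day difference in change. Use a short range of SDs that includes the pilot spread, at stated correlations (for example 0.6 to 0.8). The two rows tabulated above, plus one for the SD the sponsor can support, would be enough.
4. Qualify the statement of good power for 5 points unless 15 is supported as an SD of change.

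If data for 15 as an SD of change exist, a sentence citing them settles the first and last items. The cost is protocol wording and one revised table column. The sample size, endpoint, test and data collection stay as they are. The downside is that the stated power may be less favourable.
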